DSMP	Data Safety Monitoring Plan
eCRF	Electronic Case Report Form
END	Discharge
FDA	Food and Drug Administration
FU	Follow Up
GCP	Good Clinical Practice
ICH	International Conference on Harmonisation
IRB	Institutional Review Board
MCID	Minimally Clinical Important Difference
MSK	Musculoskeletal Pain
NIAMS	National Institute of Arthritis and Musculoskeletal and Skin Diseases
NIH	National Institutes of Health
OHRP	Office for Human Research Protections
OSF	Online Screening Form
PD	Protocol Deviation
PI	Principal Investigator
PID	Participant Identification Number
PRVR	Pain Rehabilitation Virtual Reality
PT	Physical Therapy/Therapist
REDCap	Research Electronic Data Capture
SAE	Serious Adverse Event
SCH	Stanford Children's Health
SMC	Safety Monitoring Committee
SR	Self-Report
UP	Unanticipated Problem

PARTICIPATING STUDY SITES

The study will be conducted at the Department of Rehabilitation at Stanford Children's Health (SCH) at the Pediatric Pain Management Clinic (PPMC).

PRÉCIS

Study Title

Pain Rehabilitation Virtual Reality (PRVR) Innovations to Enhance Mobility in the Presence of Pain // Pediatric Pain Rehabilitation with Virtual Reality (PRVR) Feasibility Study

Objectives

For many adolescents suffering with chronic pain, fear associated with movement and return to activities significantly interferes with clinical improvement. Prior research supports virtual reality (VR)'s ability to reduce fear of movement-related pain, provide distraction from pain symptoms, encourage increased range of motion, improve endurance, facilitate postural improvements, and enhance tolerance to sensory stimuli for desensitization. Thus, VR has vast potential to become an instrumental tool in pediatric pain rehabilitation programs.

We conducted a pilot study of the pain rehabilitation virtual reality (PRVR) platform, which included the development and feasibility testing of a number of unique VR experiences for youth undergoing chronic pain treatment and rehabilitation. With iterated improvement based on patient feedback, these VR rehabilitation experiences feature mirror therapy, exaggerated movement capabilities, biofeedback, and a Clinical Research Tool that tracks movement of each extremity in real-time with advanced analytic capabilities. Results from patients and clinicians (psychology, physical therapy, occupational therapy) in this study supported the PRVR platform as an acceptable, feasible, and useful intervention in this patient setting.

Design and Outcomes

This is a single arm feasibility study. A “**participant**” in this study is defined as a child and at least one parent. The **primary outcomes** are feasibility, acceptability, and utility of VR. The **secondary outcomes** are physical function (child only) and pain-related fear and avoidance (child).

Interventions and Duration

All participants will receive an Oculus Quest 2 virtual reality (VR) headset for use during their treatment at the PPMC. VR will supplement treatment and be used in session (either in-person or telehealth) and at home as part of their prescribed treatment homework.

Sample Size and Population

Patients who meet eligibility criteria will be referred to the study by their clinician at clinic appointments.

2. BACKGROUND AND RATIONALE

2.1 Background and Significance

Overall Scientific Premise. Chronic musculoskeletal (MSK) pain in adolescence is a significant public health concern with median prevalence rates of 11 to 38%¹⁻², with 3 to 5% of adolescents suffering from significant pain-related disability²⁵⁻²⁶, costing society \$19.5 billion annually in the US alone³. Notwithstanding the personal suffering and persistent physical and economic consequences for families, chronic pain in adolescence can predispose the development of adult chronic pain²⁷. Progressively increasing activity in the presence of pain is critical for effective functional restoration in chronic MSK pain in adolescents⁶ and adults⁷⁻¹³ with physiotherapy (PT) a critical ingredient¹⁴. Despite the widespread use of Standard Physiotherapy Rehabilitation (SPR)¹⁵, daring to increase movement while in pain can often feel physically and emotionally unattainable with fear of pain a particularly salient influence on pain outcomes¹⁶⁻¹⁹,

hindering clinical improvement²⁰. Virtual reality (VR) has the potential to break the vicious cycle of fear of movement and avoidance during PT. VR provides access to a multisensory, three-dimensional (3D) immersive experience to overcome obstacles that seem insurmountable in the real world. Thus, the current study tests pain rehabilitation virtual reality (PRVR) for adolescents with chronic MSK pain. PRVR was created with input from a multidisciplinary collaborative team of pediatric rehabilitation providers and patient end users, alongside VR technology developers in response to the growing need for VR programming specific to pediatric chronic pain populations whose mobility has been limited due to pain, fear and activity avoidance. PRVR gamifies PT, helping patients increase their range of motion and become more comfortable moving their bodies to achieve game objectives. The games offer a combination of acute distraction from pain, reinforcement of movement, and progressive increases in range of motion. With evidence that VR holds promise for chronic pain rehabilitation in adults^{23,24,28} and compelling preliminary results from our feasibility-tested immersive PRVR intervention, this feasibility study will provide the necessary findings to support or refute the feasibility of scale implementation of PRVR, a tailored treatment option for adolescents struggling with persistent MSK pain, fear, and disability.

Scientific premise for Virtual Reality. The application of VR in healthcare has rapidly accelerated in recent years due to increased market availability and declining costs. VR enables the user to interact with a computer-generated environment that harnesses sensory inputs (e.g., visual, audio, tactile) to provide an immersive experience to facilitate reaching therapeutic goals. Most commonly applied in the context of acute pain relief, research is emerging for its application in the realm of chronic pain rehabilitation. VR has been suggested as an alternative to opioids with the therapeutic mechanisms centered on distraction^{29,30}, neuromodulation of body perception³¹, and graded exposure to feared/avoided movements^{23,24,28,32}. Moreover, VR can potentially enhance motivation and engagement during physical rehabilitation, facilitate repetitive motions, and incorporate real-time and longitudinal feedback for the patient and clinician³³⁻³⁶. Perhaps most exciting is the prospect of VR to engage several cortical and subcortical neuronal circuits that potentiate learning and recovery^{37,38} with the potential for enhanced cortical reorganization^{39,40}. The extant literature includes proof of concept, feasibility, and pilot RCT studies. One recently published study of VR combined with exercise for adults with fibromyalgia demonstrated greater improvements in pain, fear of movement, fatigue, level of physical activity, and quality of life when compared to exercise alone²⁸. Overall, many studies report promising outcomes yet lack the rigor and measurement over time critical to establish VR as an evidence-based treatment for chronic pain rehabilitation.

Scientific premise for physical activity monitoring. A cycle of fear of movement and activity avoidance in adolescents with chronic pain can lead to decreased tolerance of physical activity that persists into adulthood⁴¹. Abnormal kinesics, such as asymmetry in range of motion, or timing of muscle activation or joint motions, commonly exist as a compensatory mechanism in chronic pain⁴¹⁻⁴³, potentially amplified by pain-related fear⁴⁴. This trial will include self-report, objective tests of physical function^{45,46} coupled with real world objective physical activity monitoring via a wrist-worn actigraph. Actigraphy is particularly useful as self-report measures can be prone to response shift and reporter bias^{47,48}. Unlike laboratory-based objective measures of physical activity, such as timed walks and peak oxygen consumption during exercise, actigraphy provides high ecological validity with unobtrusive measurement of activity levels during daily life⁴⁹ with adolescents with chronic pain having lower mean and peak activity levels compared to healthy peers⁴⁸.

Significance of the expected research contribution: (1) harnessing immersive technology to overcome fear of movement in the presence of pain, (2) providing real-time feedback in a gamified context to sustain motivation and adherence, and (3) purposefully capturing both objective (physical function assessment, actigraphy) and subjective (self-report) daily functioning to define clinical endpoints and assess treatment progress in the clinic and at home.

Innovation

Treatment of chronic pain remains a tremendous challenge⁵¹. Developing mechanistically informed and innovative treatment approaches results in optimal clinical care. This application shifts current research and clinical practice by: **(1) Increasing physical functioning using a motivating and gamified context with concomitant decreases in fear of pain.** PRVR targets functional improvement through harnessing the immersive and fun elements of VR gaming. Making gains in physical function and movement is not only highly reinforcing in itself, we have shown that it can lead to changes at the neural circuit level in somatosensory and motor processing while simultaneously decreasing fear of pain⁵². **(2) Leveraging digital solutions.** Emerging trends in healthcare call for a precision medicine approach⁵³ with its success contingent on the collection of patient data across domains as well as the development of efficient and effective targeted treatments. Digital health has the potential to integrally contribute to both data collection and intervention and is at the core of the current proposal. Data collected from the child (electronic daily diary, actigraphy, wearable sensors in VR) can be communicated to providers to inform clinical decision-making and support tailored, point of care decisions that result in science-forward, targeted, and effective interventions. We envision this synergistic and dynamic model (**Figure 1**; Richardson et al., *in submission*) as the future of evidence-based treatment for pediatric chronic pain. **(3) Nonpharmacological solution with the potential for brain circuit engagement.** Identifying nonpharmacological interventions for adolescents is critical as few analgesics or psychotropics have documented long-term safety and efficacy in the developing brain and opioids are known to have adverse long-term effects on the brain⁵⁴. Given we have demonstrated neural plasticity of adolescents with chronic pain after pain rehabilitation^{52,55,56} and the prospect of VR to engage cortical and subcortical neuronal circuits that potentiate learning and recovery^{37,38} and the potential for enhanced cortical reorganization^{39,40}, testing the effectiveness of VR for adolescents with MSK pain is justified. *Overall, the momentum is building in the field of VR for pain with over 100 active studies registered at ClinicalTrials.gov with this study representing the first targeting adolescents with MSK pain, thus, this proposal is timely.*

2.2 Study Rationale

Preliminary Studies/Progress Report

Preliminary Data to Support Aim 1.

(a) Human-centered design and feasibility testing of PRVR. The pediatric pain rehabilitation team at Stanford Children's Health (SCH) worked collaboratively with the Stanford CHARIOT Program and consultant **[name]** (Mighty Immersion, Inc.) to develop PRVR content, *Fruity Feet* (Griffin et al., *in submission*). *Fruity Feet* was developed using a human-centered approach with patient and clinician end-user feedback across four phases: (1) Needs Assessment, (2) Prototyping, (3) Iteration and Refinement, and (4) Feasibility and Acceptability. It was designed to be developmentally appropriate for youth by focusing on fun, while leaning on stylized graphics and encouraging in-game feedback. Gameplay mechanics were built around PT movement goals, for example for lower extremity: multiplanar stepping (i.e., forward, side, back), stomping, marching, kicking, raising leg to different heights, and active ankle range of motion tasks. Importantly, it was also built to scale to a patient's mobility, ensuring that patients

Figure 1. Transforming Healthcare with Digital Solutions

[figure not shown]
[figure not shown]
[figure not shown]

Figure 4. Fruity Feet settings. Providers can adjust the game to fit patient needs. *Intensity* affects rate fruit appears. *Left/Right Focus* encourages use of affected side. *Fruit Size* affects foot lift to stomp fruit. *Extremity Focus* focuses on lower or upper extremities. *Foot/Hand Mirroring* mirrors the virtual extremity, like mirror-therapy. *Foot/Hand Exaggeration* amplifies or decreases translation of real-world movement.

of all abilities could play the game and benefit from the VR intervention (**Figure 4**). Consistent with the recommendations for VR clinical trial methodology⁸⁰, this human-centered iterative design process yielded a program that, in addition to gamification, provides backend mechanics giving PT providers the capability to control intensity, affected side/extremity emphasis, mirroring, and movement exaggeration to leverage the potential neuromodulatory effects of VR coupled with targeted pain PT.

(b) PRVR increases movement. A prospective, randomized crossover study led by Co-Investigator **[name]** compared PRVR vs. SPR ages 6 and older, including adolescents (n=41) during a single session

Figure 5. SPR vs PRVR total movement for adult (n=24) and pediatric (n=17)

of outpatient PT with each patient serving as their own control (NCT03874507). Patients moved significantly more when participating in PRVR compared to SPR (1120.88 meters vs 672.65 meters $p = 5.47E-08$; **Figure 5**). When stratified by therapy target (upper vs lower) PRVR treatment was also associated with more movement of the appropriate limbs, lower ($p < 0.001$) and upper ($p = 0.01$). Pediatric users reported significantly less pain when using VR (88%) compared to adults (50%) and virtually all patients reported enjoying the VR experience (96% adult users; 100% pediatric users). (Caruso et al., *in preparation*). These results suggest marked increases in movement, potential pain relief, and a fun experience using VR in PT and warrants examination for cumulative effects over multiple treatment sessions.

Feasibility and Acceptability Data. PRVR feasibility testing (**Mayday Fund supported**) included 17 participants (13 female, 4 male), mean age 13.24 (range 7-17), completing a total of 63 sessions. Overall reports of immersion were high ($M = 28.98$, $SD = 4.02$ out of 40). Analysis of 45 sessions from 13 patients entered into the NVivo qualitative data analysis program revealed: 1) positive experience (i.e., enjoyed it, would like to utilize the VR program again, felt it was a helpful tool), 2) feeling distracted from pain while engaged in VR, 3) increased physical function/mobility, and 4) reduced pain behaviors/symptoms during VR (Griffin et al., *in submission*). These results suggest that Fruity Feet has the right mix of immersion, fun and PT movement capabilities to provide targeted and effective pain physiotherapy in VR.

3. STUDY DESIGN

Recruitment. Potential participants were identified at their multidisciplinary evaluation at the Pediatric Pain Management Clinic and at participating private practices. Participants will be referred by their clinician and if interested will be put in contact with [name], her co-investigators, or trained members of the research team.

Trained members of the research team may need to contact youth and caregivers to confirm eligibility after referral. Additionally, a study flyer will be posted on a bulletin board of all active clinical studies in patient waiting rooms and/or given to eligible participants if they would like.

For inclusion, the patients: 1) are 10-17 years old; 2) have musculoskeletal or neuropathic pain (e.g., localized [back, limb], diffuse)⁴⁷ not due to an acute trauma (active sprain or fracture); 3) English language proficiency.

Patient exclusion criteria are: 1) significant cognitive impairment (e.g., brain injury) and 2) significant medical or psychiatric problem that would interfere with treatment (e.g., seizures, psychosis, suicidality). 3) Presents with a condition that interferes with virtual reality usage (e.g., history of seizure, facial injury precluding safe placement of headset, visual impairment, significant hearing impairment impact ability to follow audio instructions). **Identification of Eligibility:** Patients and their parents who meet eligibility criteria will be referred to the study by their pain clinicians at clinic appointments. A trained member of the research team will reach out to the family after they are referred and they agree.

Study Procedures. After the informed assent/consent, baseline will begin, and participants will complete baseline questionnaires. Discharge testing occurs at the end of 6-8 sessions or when the clinician believes they are finished with treatment. Discharge includes participant questionnaires. At 3 months follow-up,

participants complete self-report questionnaires. VR will supplement treatment and be used in session (either in-person or telehealth) and at home as part of their prescribed treatment homework. We will ask youth and caregivers to join a training session via zoom or in person so that trained members of the research team may orientate the family to the VR equipment and help them set it up in the environment in which they will be asked to use the VR by their clinician.

Optional study procedures.

Daily Diary Surveys: Answering questions in the daily diary will take approximately 3 minutes to complete. You will be asked to fill out the daily diary and given the option to answer weekly, daily, and/or when you have PT sessions during study treatment and for one week at 3-month follow-up if you choose. You will be compensated a \$20 bonus as a thank you for your time if you choose to answer these surveys.

Brief Informational Interview: This exploratory study seeks to gather reports from participants after undergoing virtual reality exposure, paying particular attention to the language individuals use to describe their experience. Thus, the study procedure may include an informal and semi-structured interview, that will take place in the clinic after VR exposure. Participants and their parents may be asked to reflect on their condition, and on their experience with the VR module. The interviews may be recorded and transcribed. Personally-identifying information will not be disclosed from these interviews. Audio devices will be kept in a locked office at Stanford University.

Actigraph Watch: Participants can wear a small, electronic study device on your wrist that tracks your activity level and sleep. If they choose to participate in this activity, participants will be asked to wear this from the start of the study until the last study treatment session and responsible for returning this electronic study device at the end of the study treatment period.

5. STUDY INTERVENTIONS

5.1 Interventions, Administration, and Duration

Participants will complete their treatment sessions 1-hour each, delivered over ~6-12 weeks or until clinician believes the patient is done with treatment. VR will supplement treatment and be used in session (either in-person or telehealth) and at home as part of their prescribed treatment homework.

5.1.2 Compensation

All patients will be closely monitored by the PI, [name], as well as the treatment and research team. Patients are compensated for their time and contribution to this study, with increased compensation for the 3-month post-discharge follow-up. The following is the compensation timeline for all patients in the study:

- **Timepoint 1:** \$10.00 Amazon.com gift code at the start of treatment after baseline completion of questionnaires
 - \$20 bonus if participants agree to participate in the daily surveys
- **Timepoint 2:** \$20.00 Amazon.com gift code after completion of treatment and end of treatment questionnaires
- **Timepoint 3:** \$30.00 Amazon.com gift code at the 3 month post-discharge follow-up for completion of questionnaires

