5.4 Adherence Assessment

Patients will be closely monitored by the PI, [name], as well as the treatment and research team. Patients are compensated for their time and contribution to this study, with increased compensation for the 3-month follow-ups. Follow-up will occur at 3-months for both treatment groups.

6. Description of Evaluations

The Schedule of Evaluations will include Recruitment (referral), a Baseline Assessment (informed consent/assent, self-reported questionnaires), Discharge Assessment (self-report questionnaires), and a 3-month follow-up (self-report questionnaires).

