8. INTERVENTION DISCONTINUATION

Patients and their parents have the right to withdraw consent/assent or discontinue participation at any time without penalty or any impact on the child's care. Because this is an exploratory clinical

trial, we will not discontinue participation based on missed attendance to treatment sessions. There will be no temporary discontinuations from treatment or study participation. The PI may withdraw a patient/parent dyad from the study for one or more of the following reasons:

- Failure to follow instructions of the PI or study staff.
- The PI decides that continued participation would be harmful (e.g., patient reports increased emotional or physical distress from exposure therapy)

Patients and parents will be asked permission to use data collected from the study if they are asked to discontinue or decide to withdraw from the study.

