9. STATISTICAL CONSIDERATIONS

9.1 General Design Issues

To characterize feasibility of a future hybrid effectiveness-dissemination trial of PRVR in routine physiotherapy practice. Hypotheses: PRVR participants will have (1) high patient-reported treatment satisfaction and high clinician-rated patient engagement scores; Clinicians will report high clinical proficiency and self-efficacy in using PRVR.

Analysis Plan: *Satisfaction.* We will examine mean satisfaction scores, clinician rated engagement scores, and clinician proficiency and efficacy with PRVR clinical use.

Adherence/retention. We will examine mean adolescent adherence to survey completion, percent of patients who dropout prior to treatment completion, and VR side effects reported.

Health care costs and pain medication use. We will examine health care and pain medication use by calculating totals via healthcare cost surveys and compared across timepoints.

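### The Timepoint 2 payment is worded as needing completed treatment as well as questionnaires, so families who leave treatment early have no stated paid route to give end-of-treatment data

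*Combined protocol and SAP*

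**What the plan says.** Section 5.1.2 (Compensation) sets out three scheduled payments and one optional bonus:

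- Timepoint 1, $10: a "gift code at the start of treatment after baseline completion of questionnaires".
- Timepoint 2, $20: a "gift code after completion of treatment and end of treatment questionnaires".
- Timepoint 3, $30: a "gift code at the 3 month post-discharge follow-up for completion of questionnaires".
- Optional, $20: a "20 bonus if participants agree to participate in the daily surveys".

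Section 5.4 (Adherence Assessment) gives the purpose: "Patients are compensated for their time and contribution to this study, with increased compensation for the 3-month follow-ups".

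Section 3 (Study Procedures) places discharge testing after 6-8 sessions, or when the clinician judges treatment to be over. Section 8 lets families "discontinue participation at any time without penalty", says that missed sessions will not end participation, and asks those who leave for permission to use data from the study. It describes no further assessment for them.

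Section 9.1 plans mean satisfaction scores and, under adherence and retention, the "percent of patients who dropout prior to treatment completion". The Précis names feasibility, acceptability and utility as the primary outcomes of this single-arm study.

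**The concern.** Timepoint 2 is the only payment whose wording names completion of treatment. That matters in two ways.

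First, it affects who supplies data. Families who leave treatment early are plausibly less satisfied than those who finish. If they are neither scheduled for the end-of-treatment questionnaires nor paid for them, the satisfaction mean rests mostly on completers, and in a feasibility study the views of those who left are among the most useful.

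Second, it affects a reported result. The event that releases the payment, completing treatment, is also the event that defines the dropout percentage. With a single arm, no comparison group would show how much of the observed retention is due to the payment.

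**Working it through.** The plan states no sample size, expected dropout rate or response to incentives, so there is no figure of its own to reproduce. The check sets the passages side by side and computes the share of payment at stake.

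**1. Conditions attached to each payment (Section 5.1.2)**

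| Payment | Amount | Questionnaires or surveys named | Treatment completion named |
|---|---|---|---|
| Timepoint 1 | $10 | yes | no |
| Timepoint 2 | $20 | yes | yes |
| Timepoint 3 | $30 | yes | no |
| Diary bonus | $20 | yes | no |

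**2. Amount at stake for a family that leaves treatment early**

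- Scheduled total: 10 + 20 + 30 = $60. Timepoint 2 share: 20 / 60 = 33%.
- With the diary bonus: 60 + 20 = $80. Timepoint 2 share: 20 / 80 = 25%.

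**3. Who is affected**

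- Finishes treatment with VR: has a discharge assessment and is paid.
- Stops VR but finishes treatment: VR is described as a supplement to treatment, so this family still completes treatment, has a discharge assessment and is paid.
- Misses sessions but is later discharged by the clinician: missed sessions do not end participation, and the clinician's judgement can define the end of treatment. This family may well count as a completer.
- Leaves treatment before either end point in Section 3, but is willing to answer questionnaires: no discharge assessment is described and, on the plain wording, no Timepoint 2 payment. This is the affected group.
- Leaves the study altogether: supplies no questionnaires under any payment wording.

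**4. Effect on the satisfaction mean**

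Let *d* be the proportion who leave treatment early, *C* the mean satisfaction of completers and *L* the mean of early leavers. The mean over everyone is (1 − *d*)*C* + *d L*. If only completers answer, the reported mean is *C*, which differs from the full mean by

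*C* − [(1 − *d*)*C* + *d L*] = *d*(*C* − *L*).

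This is positive whenever *d* > 0 and early leavers are less satisfied. The documents give none of *d*, *C* or *L*, so the direction is plausible but the size cannot be stated.

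**5. Effect on the dropout percentage**

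A payment conditional on finishing can encourage finishing and gives no reason to leave. Any effect is therefore downward. Nothing in the documents allows it to be quantified.

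**The case against.** The strongest reply is that Section 5.1.2 is a payment timeline. Each line pairs a moment with a set of questionnaires, and the reference to finishing treatment may only say when Timepoint 2 falls. The stated purpose, time and contribution, fits that reading. This stands as a possibility. But nothing in the available text says that early leavers are paid, and staff or families could reasonably read a condition, so the line needs clarifying either way.

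Second, the consent documents (Supplemental Materials II) are not in the text available here and may contain payment terms for early leavers. This also stands, and is why the fix asks for a check against them rather than assuming a gap.

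Third, $20 after roughly 6-12 weeks of one-hour sessions is a weak inducement. Dropout is one descriptive item with no threshold attached, and Section 9.1 aims at a future trial in routine practice, where retention under research payment is itself informative. This limits the dropout point but does not answer the one about missing satisfaction data.

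Several stronger readings are tempting, and the documents do not support them:

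- A reader might infer that stopping VR forfeits the payment. The wording concerns treatment, which VR only supplements.
- A reader might infer that an early leaver also loses the $30 at Timepoint 3, making 20 + 30 = $50 of $60 (83%). Timepoint 3 is worded for questionnaires alone, and no section says that an early leaver is excluded because no formal discharge took place.
- A reader might see a breach of the no-penalty promise in Section 8. That promise concerns withdrawing consent or leaving the study, and not being paid for a milestone not reached is not clearly a penalty.

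**Conclusion.** The point holds as a cheap improvement to wording and data collection. It does not show that the results will be biased by any stated amount. On the plain reading, families who leave treatment early but would still answer questionnaires have neither a scheduled end-of-treatment assessment nor a payment for one. The supportable loss is $20: 33% of scheduled payments, or 25% with the diary bonus.

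The conclusion that satisfaction data will tend to come from completers assumes that some families leave early and that no unseen document already provides for them. That this would flatter the satisfaction mean assumes further that early leavers are less satisfied. The effect on the dropout percentage has a known direction only. It would be too much to say that the dropout rate measures the payment rather than the appeal of VR.

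**What to change.** Four linked changes:

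1. Reword Timepoint 2 along these lines: *$20.00 gift code for completing the end-of-treatment questionnaires, whether or not treatment was completed.*
2. In Section 3 and the Discharge Assessment text of Section 6.2, say that these questionnaires are also offered to families who leave treatment early but remain willing to give data, and say when. Without this, the new payment wording would have no assessment to attach to.
3. State that Timepoint 3 is open to those families on the same terms, and from what date the three months are counted when there was no formal discharge.
4. Check that the consent and assent text agrees.

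The cost is an IRB wording amendment, $20 for each early leaver who returns the end-of-treatment questionnaires, and some coordinator time. The $30 at Timepoint 3 is, on its present wording, already payable for questionnaires. The reported dropout and satisfaction figures may come out slightly less favourable. No treatment, session schedule or clinical decision changes.
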